2.1.3 Completion and Discontinuation

A patient is considered to have completed the study when he/she ceases active participation in the study because the patient has, or is presumed to have, completed all study procedures according with the protocol (with or without protocol deviations). Any other cases are classified as discontinuation.

Reasons for early termination will be reported on the Completion/Discontinuation electronic case report form (eCRF), including:

- Adverse Event
- Clinically significant change in laboratory parameter
- Protocol violation
- Pregnancy
- Patient or any legal representative requests to withdraw from the study
- Sponsor or Investigator terminates study
- Other

Regardless of the reason, all data available for the patient up to the time of completion/discontinuation should be recorded on the appropriate eCRF.

2.2 Patient Disposition

Patient disposition will be summarized by treatment group and will include:

• Number of patients who signed informed consent (enrolled)

- Number of patients who screen fail. These patients will also be summarized by primary reason for screen failure from the study. The percentage associated with each reason will have the total number of patients who screen fail as the denominator.
- Number of patients eligible for randomization. This will be calculated by taking the number enrolled minus the number of screen failures.
- Number of patients randomized
- Number of patients treated with study treatment (SS)
- Number of patients in the FAS
- Number of patients in the PPS. Patients included in the FAS but excluded from the PPS will be summarized by reason for removal (missing Holman Index measurement at baseline and/or one other timepoint, did not receive a minimum of 7 days of ILE treatment, or protocol deviation). The denominator for the percentage will be based off of the total number of patients excluded.
- Number of patients who completed the study in the FAS
- Number of patients who discontinued (withdrew early) from the study in the FAS. These patients will also be summarized by primary reason for withdrawal from the study. The percentages associated with each reason for early withdrawal will have the total number of patients who withdrew early as the denominator.

A listing of all patients enrolled in the study will be created including patient ID, age (in months), sex, treatment group, whether the patient is in each of the analyses sets, completion status, reason for discontinuation (if applicable), and the number of days that the patient remained in the study. The number of days the patient was in the study will be calculated using the following:

(Date of Study Completion/Discontinuation – Date of Informed Consent) + 1

2.3 Demographics and Other Baseline Characteristics

Demographics and other baseline characteristics will be summarized descriptively by treatment group for the FAS population. Listings will also be provided for this population.

2.3.1 Demographics

Demographics including sex, race, and ethnicity will be summarized descriptively by treatment group. Age will be summarized by age group and treatment as follows: Pre-

Term Neonate (GA in weeks, age at consent in days), Full Term Neonate (GA in weeks and days, age at consent in days), Infant (age at consent in months), Child (age at consent in years), Adolescent (age at consent in years). Diagnosis for PN will also be included in this summary.

To calculate gestational age, gestational age (weeks) will be added to gestational age (days)/7 to get the gestational age in weeks.

2.3.2 Medical History

Medical history will be coded using the Medical Dictionary for Regulatory Activities (MedDRA) and summarized by treatment group. Medical history will also be listed.

2.3.3 Prior and Concomitant Medications (Mother and Child)

Prior and concomitant medications for both mother and child will be summarized using WHODrug Anatomical Therapeutic Chemical (ATC) class level 4 and PT by treatment group. A listing will also be prepared.

2.3.4 Concomitant Procedures

Concomitant procedures will be listed only.

2.3.5 Other Baseline Characteristics

Baseline characteristics will be summarized descriptively by treatment group and stratified by age groups: a. Pre-Term Neonate, b. Full Term Neonate, c. Infant, d. Child, e. Adolescent as follows:

- length (a and b) height (c, d, e)
- head circumference (a, b, c)
- weight (a, b, c, d, e)
- body mass index (d and e)
- birth weight (a and b)

2.4 Endpoint Analyses

2.4.1 Primary Endpoint

The primary efficacy analysis will be carried out on the FAS with a supportive analysis performed on the PPS.

2.4.1.1 Derivation of Primary Endpoint

The primary endpoint is the incidence of EFAD which is defined in the protocol and will be derived based on the Holman Index (Triene/Tetraene Ratio) provided by the central laboratory.

- Holman Index <0.2: normal EFA
- Holman Index 0.2 0.4: at risk for EFAD
- Holman Index >0.4: EFAD

A patient will be considered 'at risk for developing EFAD' if they have a Holman Index of 0.2 - 0.4 at any timepoint during the study treatment.

A patient will be considered as an incident of EFAD (the 'event') if they have a Holman Index >0.4 at any timepoint during the study treatment.

For time to EFAD Kaplan Meier analyses, the index time will be the start of treatment. The first incident of EFAD will be considered the event and will use the date of EFAD (date first lab with Holman Index >0.4 reported). Patients will be censored if they do not develop EFAD during their follow-up or if they die before developing EFAD at the time of their last Holman Index laboratory measurement. Time to EFAD will be calculated for each patient who develops EFAD as follows and standardized to days:

The incidence rate of EFAD (events per 100 patient days) will be calculated as the following per treatment group:

```
Number of patients developing EFAD * 100
Total patient days
```

The total number of patient days will be calculated per treatment group as follows:

$$\sum_{i=1}^{n} (Date of First EFAD Occurrence or End Date of Treatment)$$

- Start Date of Treatment)_i + 1

Where n is the total number of patients per treatment group. If a patient develops EFAD, then the date of first EFAD occurrence will be used, and if they do not, then end date of treatment will be used. If more than one instance of EFAD occurs, the patient will be counted once and the date of first occurrence will be used. This will then be standardized to days.

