6.8.4 Holman Index >0.4 at baseline

Some study patients (especially premature infants) may demonstrate FA profile and Holman index compatible with EFAD at baseline due to their limited fat stores. The treatment for these infants is to administer EFA via ILE as part of their PN as described in Table 4, Dosing Schedule and being sure to reach the maintenance dosage. Infants with EFAD at baseline are to be followed regularly (approximately every 15 days) while receiving ILE per study protocol for improvement in their FA profile and Holman Index.

• If the Holman Index does not decrease with lipid administration in accordance with Table 4, Dosing Schedule, the patient may have greater than normal

requirements for EFA and the LA intake should be increased to the maximum dosage according to Table 4, Dosing Schedule and at the investigator's discretion.

- If the patient still does not respond, the investigator will be unblinded to determine if the patient is receiving Clinolipid or Intralipid. If the patient is receiving Clinolipid, the patient should be switched to Intralipid (as Intralipid contains a higher concentration of LA than Clinolipid).
- If the patient does not respond to Intralipid at maximal lipid dosage, consider increasing the LA intake with an enteral/oral source of LA or some additional intravenous Intralipid intakes.

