9.3 Analysis Populations

The analysis sets in this study include: the Full Analysis Set (FAS), the Per Protocol Set (PPS), and the Safety Analysis Set. The FAS includes all patients who are randomized to receive either Clinolipid or SOC SO-based lipid emulsion (Intralipid), consistent with the intention-to-treat principle. The PPS includes a subset of patients in the FAS who have Holman Index measurements taken at baseline and at least 1 other time point postbaseline, who have received a minimum of 7 days of ILE treatment, and are without a major protocol violation (i.e. violation that potentially impacts the primary endpoint). The Safety Analysis Set includes all patients that have received treatment (Clinolipid or SOC).

Subgroup analyses of patients by age group (e.g., premature infants born <37 weeks of gestation up to 1 month CA, full-term neonates born \geq 37 weeks of gestation <1 month of age, infants 1 to <12 months of age, children 1 to <10 years of age, adolescent 10 to <18

years of age) and subgroup analyses for neonates according to GA and BW will be conducted.

The primary endpoint analysis and secondary endpoint analyses of liver disease including parenteral nutrition-associated liver disease (PNALD) and the adequacy of nutritional intervention will be conducted for both the FAS and PPS. All safety analyses will be conducted on the Safety Analysis Set.

Infants found to subsequently have baseline EFAD will not be considered to have treatment emergent EFAD and will be analyzed separately from infants with normal baseline EFAD status. Unblinded infants will be analyzed separately as well.

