9.5 Primary Endpoint

The primary endpoint is the risk of developing EFAD defined as defined by Figure in Appendix 3.

- The risk of developing EFAD in pediatric patients will be summarized by treatment group as frequency and percentage. Time to developing EFAD will be analyzed using the Kaplan-Meier approach.
- Both incidence rate and proportion of EFAD will be computed for each treatment group.
- The incidence rate of EFAD will be computed as the number of patients who develop EFAD during the Study Treatment Period divided by the corresponding person time (i.e. "person-day" which is computed as "total number of patients" times "treatment exposure period [day]" in the corresponding treatment group), and reported as per 100 patient days.
- The proportion of EFAD will be computed as the number of patients who develop EFAD during the Study Treatment Period divided by the corresponding total number of patients.

- The Holman Index will be summarized with descriptive statistics (number of patients, mean, standard deviation, median, minimum, and maximum) on an approximately 15-day basis in each of the 2 treatment groups (Clinolipid vs Intralipid).
- FA profiles will be summarized using descriptive statistics (number of patients, mean, standard deviation, median, minimum, and maximum) in each of the 2 treatment groups (Clinolipid vs Intralipid), as well as descriptive statistics of genetic polymorphisms in the FADS1 and FADS2 genes.

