2.4.1.2 Analysis of Primary Endpoint

Holman index scores will be summarized descriptively by timepoint per treatment group using n, mean, standard deviation, minimum, Q1, median, Q3, and maximum.

The frequency and percentage of patients at risk of developing EFAD (Holman Index 0.2-0.4) as well as those who developed EFAD (Holman Index >0.4) will be summarized by timepoint and at the maximum by treatment group. The denominator for the percentage of patients will be the number of patients in the population who had at least one post-baseline Holman Index measurement available. The incidence rate (per 100 patient days) of EFAD will also be calculated per treatment group.

If there are more than 5 cases of EFAD per arm, then time to develop EFAD will be analyzed using survival analysis approach (cumulative incidence), and the mean, standard error, Q1, median, Q3, minimum, and maximum for each treatment group will be displayed, where calculable. A cumulative incidence plot will also be produced. If there are less than 5 cases of EFAD in each treatment arm, then time to developing EFAD will be summarized descriptively by treatment group using n, mean, standard deviation, minimum, Q1, median, Q3, and maximum. If no events occur, then time to EFAD will not be calculated.

A spaghetti plot consisting of Holman index values over time will be produced with one line representing each patient, and different types of lines or symbols (e.g. solid and dashed) representing each treatment group. Two bolded lines will be added at y=0.2 and y=0.4 to represent the bounds for being at risk of EFAD and developing EFAD.

As a supportive analysis to the primary endpoint, the following will be analyzed:

• FA profiles will be summarized using descriptive statistics (number of patients, mean, standard deviation, median, minimum, and maximum) in each of the 2 treatment groups (Clinolipid vs Intralipid), as well as descriptive statistics of genetic polymorphisms in the FADS1 and FADS2 genes for the patients with buccal swabs with the 5 highest and 5 lowest arachidonic acid values in each treatment group.

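### The SAP event rule has no baseline condition, so persisting baseline EFAD is counted as new EFAD, which Protocol 9.3 rules out for infants

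*SAP*

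**What the plan says.** **Event rule.** Under SAP 2.4.1.1 a patient is an incident case "if they have a Holman Index >0.4 at any timepoint during the study treatment". The event is dated at the first sample above 0.4, and patient-days stop at that date. The rule does not mention the baseline value.

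**Reporting.** SAP 2.4.1.2 takes as denominator the "number of patients in the population who had at least one post-baseline Holman Index measurement available". Counts are "summarized by timepoint and at the maximum by treatment group".

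**Protocol rule on baseline deficiency.** Protocol 9.3 states: "Infants found to subsequently have baseline EFAD will not be considered to have treatment emergent EFAD and will be analyzed separately" from infants whose baseline status is normal.

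**Such patients are expected.** Protocol 6.8.4 says that some patients, premature infants above all, "may demonstrate FA profile and Holman index compatible with EFAD at baseline due to their limited fat stores". It continues: "Infants with EFAD at baseline are to be followed regularly (approximately every 15 days) while receiving ILE per study protocol".

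**Protocol denominator.** Protocol 9.5 defines the proportion as the "number of patients who develop EFAD during the Study Treatment Period divided by the corresponding total number of patients".

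**Declared changes.** SAP 3 declares no departure from the protocol's analyses.

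**The concern.** The primary objective is the risk of developing EFAD. A patient who is already above 0.4 before treatment cannot develop it in that sense until the index has first come down. If such a patient is still above 0.4 at the first on-treatment sample, the SAP rule records a new case with an event date, even when the index is falling.

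These patients would then enter all three primary summaries as new cases: the proportion, the rate per 100 patient-days and the time to EFAD. No hypothesis test is planned, so the reported proportion and rate are themselves the result.

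Equal persistence in the two arms would raise both figures without opening a gap between them. Slower resolution in one arm would be a genuine finding, but it would be about recovery from deficiency and would be reported as new onset.

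**Working it through.** **Step 1: one infant under both rules.** Baseline index 0.6, Day 15 index 0.5, on study lipid throughout.

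- SAP 2.4.1.1: 0.5 > 0.4 during study treatment, so this is an incident case dated at Day 15.
- Protocol 9.3: EFAD was present at baseline, so this is not treatment-emergent and belongs in a separate analysis.

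**Step 2: does other SAP text restore the protocol rule?**

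- The denominator (2.4.1.2) needs one post-baseline value only.
- Patient-days (2.4.1.1) are summed over all patients in the group.
- The per protocol set (1.5.1) needs a baseline index to exist, not to be 0.4 or below.
- The sensitivity analyses (2.4.1.3, 2.6.5) concern pre-randomization lipid and the per protocol set.
- No table title in SAP Appendix 1 refers to baseline EFAD.

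**Step 3: illustration of size.** The documents fix only 50 patients per arm. The following are assumptions:

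- q = 2%, true new onset among patients not deficient at baseline
- π = 10%, baseline EFAD among infants, and none in older patients
- f = infant share of the arm, so p = f × π is the share of the arm deficient at baseline
- s = share of those still above 0.4 on treatment

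Reported proportion = q(1 − p) + p × s. The at-risk proportion is q = 2%.

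| f | p | s = 25% | s = 50% | s = 75% |
|---|---|---|---|---|
| 50% | 0.05 | 3.15% | 4.40% | 5.65% |
| 80% | 0.08 | 3.84% | 5.84% | 7.84% |
| 100% | 0.10 | 4.30% | 6.80% | 9.30% |

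For example, p = 0.10 and s = 50% gives 0.02 × 0.90 + 0.10 × 0.50 = 0.018 + 0.050 = 6.8%.

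**Step 4: rate per 100 patient-days.** Assume also 30 treatment days, events at Day 15 and s = 50%.

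| p | SAP events / days | SAP rate | At-risk events / days | At-risk rate | Ratio |
|---|---|---|---|---|---|
| 0.05 | 2.2 / 1467 | 0.150 | 0.95 / 1410.75 | 0.067 | 2.2 |
| 0.08 | 2.92 / 1456.2 | 0.201 | 0.92 / 1366.2 | 0.067 | 3.0 |
| 0.10 | 3.4 / 1449 | 0.235 | 0.9 / 1336.5 | 0.067 | 3.5 |

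SAP days at p = 0.10: 3.4 × 15 + 46.6 × 30 = 51 + 1398 = 1449.

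**Step 5: numerator or denominator?** At p = 0.10, removing baseline cases from the numerator only gives 0.9/50 = 1.8% and 0.9/1486.5 days = 0.061 per 100. Removing them from both gives 2.0% and 0.067. The SAP rule gives 6.8% and 0.235. The numerator rule is what matters.

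**Step 6: whole-patient examples.** One new case and one persisting baseline case: 2/50 = 4.0% under the SAP, against 1/49 = 2.0%. One new case and five persisting baseline cases: 6/50 = 12.0% (exact 95% CI 4.5 to 24.3), against 1/45 = 2.2% (0.1 to 11.8).

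**Step 7: sensitivity to new onset.** The excess is q(1 − p) + p × s − q = p(s − q). At p = 0.10 and s = 50%:

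| q | SAP proportion | Excess (points) | Ratio |
|---|---|---|---|
| 2% | 6.8% | 4.8 | 3.4 |
| 5% | 9.5% | 4.5 | 1.9 |
| 10% | 14.0% | 4.0 | 1.4 |
| 20% | 23.0% | 3.0 | 1.15 |

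**Step 8: choice of method.** SAP 2.4.1.2 says: "If there are more than 5 cases of EFAD per arm, then time to develop EFAD will be analyzed using survival analysis approach". At q = 2% and s = 50%, the chance that one given arm exceeds five cases under the SAP rule is 7.7% at p = 0.10 and 56% at p = 0.20. Requiring both arms to do so gives 0.0774² = 0.6% and 0.558² = 31%. The effect on method choice is small at 10% prevalence.

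**The case against.** The best defence is that the SAP omits the protocol rule without overriding it. SAP 2.4.1.1 says that EFAD is defined in the protocol, SAP 3 declares no changes, and the text speaks of patients who develop EFAD. A careful analyst could therefore still apply Protocol 9.3. That is possible, but the same section then gives an explicit rule without a baseline condition, and that rule is what would be programmed. At best, two analysts could obtain two different primary results.

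Other points have some force:

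- **Unseen definition.** Protocol 9.5 refers the endpoint definition to a figure in Appendix 3 that is absent from the copy reviewed, and it might carry a baseline branch. Protocol 9.3 is explicit in any case.
- **Recoverability.** By-timepoint tables may show how many patients exceed 0.4 at baseline; the spaghetti plot and Listing 16.2.8.1.1 would show individuals. Only table titles are given, so a table might hold baseline rows. None of this takes the patients out of the primary count.
- **Size.** No document figure supports 2% new onset, and the fold-changes depend on it (Step 7). Prevalence and persistence could also be low, since standard lipid may be given before screening. This objection stands: the figures show direction and mechanism, not an expected bias.
- **Cut-off.** Protocol 9.3 contrasts baseline EFAD with normal status, and Protocol 6.8.1 calls only values below 0.2 normal. But both documents place EFAD above 0.4, so a patient at 0.2 to 0.4 does not have it yet and can still develop it.
- **Age.** Protocol 9.3 names infants only. For older children the protocol's analysis section is silent, so the direct contradiction is confined to infants.

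**Conclusion.** The concern holds. Followed literally, the SAP places infants with persisting baseline deficiency in the primary proportion, the incidence rate and the time to EFAD as new cases. Protocol 9.3 excludes this, and SAP 3 does not declare the departure.

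The size cannot be determined from the documents, which give no baseline prevalence, persistence, new-onset risk or infant share. It is zero if no patient has baseline EFAD. Under the illustrative assumptions (2% new onset, 10% of infants affected, half persisting) the reported proportion is 4.4% to 6.8% instead of 2%, and the rate is 2.2 to 3.5 times the at-risk rate. The relative inflation falls as true new onset rises.

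The case for correction rests on the conflict over who counts as a primary event, not on these figures. It should be resolved before the endpoint is programmed.

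**What to change.** In SAP 2.4.1.1 and 2.4.1.2:

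1. Define the primary event as the first post-baseline Holman Index above 0.4 in a patient whose baseline index is 0.4 or less. State that the sample designated as baseline never counts as an event. This is needed because baseline laboratory samples may be drawn up to 24 hours after the first dose.
2. Use this at-risk group for the denominator, patient-days and time to EFAD, and reconcile it with the total number of patients in Protocol 9.5.
3. Tabulate baseline-EFAD patients separately by arm, resolved or not, and keep the all-patients count as a supportive row.
4. Apply the rule at all ages for consistency, declared as an extension of Protocol 9.3.
5. Report patients with a missing baseline index in their own row, outside the primary at-risk group, with a sensitivity analysis that includes them. The screening fallback in SAP 2.1.1 cannot help, because no fatty acid sample is scheduled at screening.
6. Report how many baseline samples were drawn after the first dose, since membership of the at-risk group then depends on a post-randomisation value.

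The cost is SAP wording, a short clarification between Protocol 9.3 and 9.5, and one extra table per analysis set. No new data are needed. The primary denominator shrinks slightly, for example to 45 from 50 per arm if 10% have baseline EFAD. The supportive row preserves the all-patients result and covers the late-baseline problem.

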6.14 Removal of Patients from the Study/ Discontinuation of the Study

Any patient/legal representative may voluntarily withdraw consent for continued participation and data collection at any time during the course of the study. The Investigator may terminate a patient's study participation at any time during the study if the Investigator judges it to be in the patient's best interest.

Patients may be withdrawn or prematurely discontinued from the study treatment/assessments for any of the following reasons:

- Adverse Event(s)
- Clinically significant change in a laboratory parameter
- Protocol violation (i.e. patient failed to meet protocol entry criteria or did not adhere to the protocol requirements)
- Pregnancy
- Patient or any legal representative requests to withdraw from the study
- Sponsor or Investigator terminates the study

All patients randomized to Clinolipid who must receive Intralipid for rescue therapy purposes will be discontinued from the trial.

Parenteral nutrition therapy may be interrupted and restarted (based on the initial randomization) within a 1 to 2-day window, subject to adjudication from the medical monitor who conducts a clinical review of current patient status, assessment of any potential AE/SAEs, discussion/clarification with the investigator to resume or abort study treatment. The outcome of the adjudication process will not preclude the monitoring for AE/SAEs for the subsequent 30 days and in the event of an AE, following the subject until the AE resolves, stabilizes or the subject returns to baseline. If there is a likelihood that the patient will require restart of PN within 1 to 2 days of the initial stoppage, then it is recommended to delay performing the End of Study Treatment procedures. However, the End of Study Treatment procedures should be completed within 2 days of the initial stoppage if the patient has not restarted PN, as per Section 7.2.4 and Appendix 1 Schedule of Events.

If a patient's participation is discontinued, the reason(s) must be recorded in the source documents and in the CRF.

End of study treatment procedures should be performed when a patient withdraws or is discontinued from the study.

Patients who are withdrawn from the study will not be replaced.

The study may be discontinued:

- If new safety information becomes available indicating that continuing the study treatment or procedures may jeopardize the safety of the patients
- Because of an administrative decision by the Sponsor

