7.2.3 Standard-of-Care Procedures

The following procedures will be performed at intervals determined by the SOC at each investigational site (refer to Appendix 1, Schedule of Events Table):

- Laboratory evaluations including:
 - hematology complete blood count
 - chemistry basic metabolic panel and electrolytes
- Diagnosis of neonatal morbidities including bronchopulmonary dysplasia (BPD), retinopathy of prematurity (ROP), intraventricular hemorrhage (IVH), periventricular leukomalacia (PVL), necrotizing enterocolitis (NEC), and late-onset sepsis in enrolled premature infants born at 24 to <37 weeks of gestation up to 1 month CA with a birth weight ≥750g.

7.2.4 Days 15, 30, 45, 60, 75 and 90 or End of Study Treatment Procedures

The Study Treatment Period starts when the patient receives study treatment. End of study treatment is defined as the last day of PN with Intralipid or Clinolipid; maximum 90 days of study treatment is allowed.

The following procedures will be performed approximately every 15 days ± 2 days for patients continuing on PN (days 15, 30, 45, 60, 75 and 90) and within ± 2 days of the last day of study treatment (maximum 90 days on either Clinolipid or Intralipid) whenever that occurs:

- Physical examination including weight, length or height (and head circumference for infants <1 year of age)
- Vital signs
- Concomitant medications
- Concomitant procedures
- AEs
- Laboratory evaluations including:
 - Hematology parameters
 - Serum chemistry parameters
 - Hepatic integrity parameters
 - Total and direct bilirubin
 - Triglyceride levels
 - FA profile
 - Holman Index
 - Phytosterol, cholesterol, and squalene levels

In addition, the following data will be collected at end of study treatment:

 Diagnosis of neonatal morbidities including bronchopulmonary dysplasia (BPD), retinopathy of prematurity (ROP), intraventricular hemorrhage (IVH), periventricular leukomalacia (PVL), necrotizing enterocolitis (NEC), and lateonset sepsis in enrolled premature infants born <37 weeks of gestation up to 1 month CA.

After end of study treatment (maximum of 90 days), the patient will receive nutritional intervention as prescribed by their healthcare provider as SOC if PN is still required.

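### Time to EFAD dates each case at its first positive sample, so with an extra sample at treatment stop the Kaplan-Meier reads too high on visit days, more so in an arm that stops PN earlier

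*SAP*

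**What the plan says.** SAP 2.4.1.1 sets the clock: "For time to EFAD Kaplan Meier analyses, the index time will be the start of treatment". For the event, the analysis "will use the date of EFAD (date first lab with Holman Index >0.4 reported". Patients without EFAD are censored "at the time of their last Holman Index laboratory measurement".

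Protocol 7.2.4 and Appendix 1 fix when the Holman Index is measured: "approximately every 15 days ± 2 days for patients continuing on PN", and again "within ± 2 days of the last day of study treatment (maximum 90 days on either Clinolipid or Intralipid) whenever that occurs". Protocol 6.14 extends the second rule to early leavers: "End of study treatment procedures should be performed when a patient withdraws or is discontinued from the study".

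Protocol 9.5 plans Kaplan-Meier for time to EFAD without condition. SAP 2.4.1.2 makes it conditional: with more than 5 cases per arm, "time to develop EFAD will be analyzed using survival analysis approach (cumulative incidence". SAP 1.6.1 lists time to EFAD as supportive of the primary endpoint. The planned sensitivity analyses concern the pre-randomization lipid (SAP 2.4.1.3) and the per-protocol set (SAP 2.6.5). Neither document mentions interval censoring.

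**The concern.** With fixed visits only, dating events at the first positive sample delays them, but the Kaplan-Meier is about right on each visit day. The sample triggered by stopping changes this.

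Suppose a patient stops between visits with EFAD that no one has yet measured. The case is found at once and counted against a risk set of patients who have not been sampled since the last visit. Those patients' own hidden cases are not yet visible, so the hazard step on that day is too large for what is known about the others. At the next visit the remaining patients contribute the whole interval's cases. Part of the interval's risk is therefore counted twice.

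The excess grows with the rate of stopping. Two arms with the same EFAD risk would show different curves if one leaves PN sooner. The trial is descriptive, with no formal test (SAP 1.4.2, 2.6.4), so a displayed curve would be read at face value.

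**Working it through.** **From the documents.** Event date, censoring date and origin (SAP 2.4.1.1). Samples every 15 ± 2 days and at stop (Protocol 7.2.4). 50 patients per arm (SAP 1.4.2). PN expected for at least 7 days (Protocol 4.2), used here as the earliest stop.

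**Assumed, because the documents give no value.** Constant EFAD hazard h = 0.004 per day. Stopping unrelated to EFAD, at constant rate L after Day 7, with median PN of 14, 21 or 28 days, so L = ln 2/7, ln 2/14 or ln 2/21. EFAD persists until sampled.

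**1. Plan's own figure.** There is none to reproduce: no EFAD rate, PN duration or event count is stated.

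**2. Formula.** Let F(c) be the chance of onset within c days of the last visit, about h·c. On day c the curve takes a step of about L·F(c), because only stoppers are sampled. At the next visit it takes the full interval factor. The cumulative hazard over an interval is therefore 15h + ∫L·F(c)dc, where 15h alone is correct.

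- Days 0-15, stops from Day 7: 15h + L·h·(15² − 7²)/2 = 0.06 + L × 0.004 × 88
- Days 15-30: 15h + L·h·15²/2 = 0.06 + L × 0.004 × 112.5, an inflation factor of 1 + 7.5L

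**3. Numbers at Day 30.** True risk = 1 − exp(−30 × 0.004) = 11.3%.

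| Median PN | L | First gap | Second gap | Formula, 1 − exp(−sum) | Simulated SAP rule |
|---|---|---|---|---|---|
| 14 days | 0.0990 | 0.0949 | 0.1046 | 18.1% | 17.5% |
| 21 days | 0.0495 | 0.0774 | 0.0823 | 14.8% | 14.4% |
| 28 days | 0.0330 | 0.0716 | 0.0749 | 13.6% | 13.4% |

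The simulation used 400,000 patients per scenario. The formula runs slightly above it, as expected from whole-day rounding and the approximation F(c) ≈ h·c.

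**4. Cause.** Removing only the stop sample brings the simulated Day-30 values back to 11.3-11.6%.

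**5. Where the curve is not too high.** On Day 14 it reads 1.0-2.8% against a true 5.4%. On Day 29 it reads 11.7%, 8.9% and 7.9% against 11.0%.

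**6. Other assumptions.**
- Hazard 0.002 per day: a true Day-30 risk of 5.8% reads 7.0-9.0%.
- True 90-day risk of 20%, constant hazard: the true Day-30 risk of 7.2% reads 13.5, 10.4, 9.1, 8.4 and 8.0% for mean treatment of 14, 21, 30, 45 and 60 days.
- Same risk, with visits jittered by ± 2 days: Day 32 reads 12.6, 10.0, 8.9 and 8.2% against 7.6% for means of 14, 21, 30 and 45 days.

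**7. Gap between arms of equal risk.** For medians of 14 and 21 days the large-sample gap at Day 30 is 17.5 − 14.4 = 3.1 points. At 50 per arm the mean gap was 2.5 points, with an SD of 14 points.

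**The case against.** **The curve may never be drawn.** Under the SAP's more-than-5-cases condition, and with the hazard above, the expected proportion with observed EFAD is 6.6%, 10.0% and 12.9% for median PN of 14, 21 and 28 days. The chance that a single arm of 50 exceeds 5 cases is then 11%, 38% and 64%. For one arm at 14 days and the other at 21, both exceed it in about 4% of trials (0.11 × 0.38). This stands, with two limits: the protocol has no such condition, and a higher or front-loaded risk would trigger the analysis more often.

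**A reader might infer that the whole curve overstates EFAD risk.** The documents do not support that. The excess is on visit days and at the end of the curve; step 5 shows it can read low just before a visit.

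**A reader might infer that the comparison of arms, or the primary result, is unsound.** That goes too far. The false gap is small beside the noise at 50 per arm, no test is planned, and the simple proportion with EFAD does not pass through this calculation.

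**A reader might carry the finding over to time to PNALD** (SAP 2.4.2.2.1), which uses a similar dating rule. Liver tests are also drawn at standard-of-care times (Protocol Appendix 1). That is a different sampling pattern, and no size was computed for it.

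**The size rests on assumptions.** This stands. EFAD that resolves between samples would push the estimate the other way.

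**Conclusion.** The plan treats interval-censored onset as exactly dated, and the sample at treatment stop turns that into an upward bias on visit days and at the end of the curve. The direction, and the dependence on earlier stopping, follow from the SAP's dating rule and the protocol's sampling schedule, provided that stop times are spread between visits and unrelated to EFAD and that EFAD persists until sampled.

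The size depends on values the documents do not give. It is material when PN is short (11.3% read as about 17.5% at a median of 14 days) and slight when it is long (7.2% read as 8.0% at a mean of 60 days). The fault is confined to a supportive analysis that the SAP may not run. It is worth correcting before database lock, but it does not threaten the main summary of EFAD.

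**What to change.** In SAP 2.4.1.1 and 2.4.1.2:

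- Define each EFAD case by the interval from the last sample with Holman Index ≤0.4 (excluded) to the first sample with Holman Index >0.4 (included), using sample collection dates.
- Keep patients without EFAD right-censored at their last Holman Index sample, as now.
- Estimate cumulative EFAD risk by arm at the scheduled visit days with an interval-censored piecewise-exponential model, with constant hazard within each 15-day interval.
- Keep the Turnbull estimator or the planned Kaplan-Meier as a sensitivity analysis.
- Do not quote a mean time to EFAD.
- Show treatment duration by arm beside the curve.

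The piecewise model is preferred as the main estimate because of the sample size. In simulations at 50 per arm with a true Day-30 risk of 11.3%, it gave 11.6%, 11.7% and 10.9% for median PN of 14, 21 and 28 days. Turnbull gave 15.7%, 12.8% and 12.6%, with a larger SD.

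The cost is SAP wording and programming; sampling, data collection and patient care do not change. The downside is a mild assumption about the hazard within each 15-day interval. If the hazard is strongly front-loaded, a small bias remains: at 50 per arm, with mean treatment of 14 and 30 days, the model gave 27.2% and 26.0% against a true 25.5%, where the planned Kaplan-Meier gave 40.4% and 30.7%.
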